Assessment day (day 2): See Figure 1 for an overview of the assessment activities.

[figure not shown]

Figure 1. Diagram of experimental protocol.

Upon arriving to start the second day of testing, participants' blood glucose level was assessed via a glucometer (CVS Health Advanced Blood Glucose Meter, United States) to ensure that their blood glucose fell within the 70-115 mg/dL guideline to exercise safely. Following this, participants were outfitted with a polar heart rate monitor (Model H7, Polar Electro, Finland) to assess heart rate during the experimental condition and then were prepared for neuroelectric testing. Participants were subsequently seated in a sound-attenuated testing chamber approximately 1 m away from the computer monitor where they completed tests of inhibitory control and sustained attention while behavioral and neuroelectric measures were assessed. Once the pretest cognitive assessment was completed, participants were administered solution into their intranasal mucosa.

Using a double-blind, placebo-controlled approach; identical vials of saline solution and Novolog insulin aspart 100 mg/mL were obtained differentiated only by the color of the stopper top, and labeled as investigational drug A and investigational drug B. All participants were administered 6 doses of 0.2 mL of solution via the LMA MAD Nasal Intranasal Mucosal Atomization device into alternating nostrils with a total administration volume of 1.2 mL. The dose of intranasal insulin was controlled by varying the number of doses which contained saline relative to the doses which contained Novolog insulin aspart 100 mg/mL (see Figure 2). The experimenters were aware of the number of doses of investigational drug A and investigational drug B administered; but were unaware which solution or stopper top was associated with insulin or saline. Following administration of the solution, participants completed the sitting/exercise experimental conditions.

Figure 2. Illustration of the intranasal insulin dosing protocol.

Active Comparator: Passive Control. The sitting experimental condition consisted of a 20 min duration where participants sat in a chair (HR = 73.2 bpm [95% CI: 70.3 to 76.2]).

Intervention. The exercise experimental condition consisted of similar 20 min duration of exercise on a motor-driven treadmill at an intensity between 60 and 65% of maximum heart rate achieved during the test of maximal oxygen uptake (HR = 118.1 bpm [95% CI: 116.2 to 120.1]).

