During both the sitting and exercise experimental conditions, participants watched an emotionally neutral video (minutes 65-85 from Wonders of the Universe (*Wonders of the Universe*, 2011)). Midway through the sitting and exercise experimental conditions and again 5 minutes following the completion of the experimental conditions, peripheral blood glucose was assessed via a glucometer. If peripheral blood glucose fell below 70 mg/dL, testing was immediately discontinued for all measures. Following the peripheral blood glucose assessment, participants again completed the tests of inhibitory control and sustained attention while behavioral and neuroelectric measures were assessed. Finally, upon completion of the cognitive assessments, participants completed a symptom survey which assessed potential side effects of intranasal insulin that participants might have experienced at any time during the experimental protocol and if participants were still experiencing those symptoms.

Measures:

Safety of Intranasal Insulin: The safety of intranasal insulin in combination with exercise was assessed by examining the incidence of participants reporting potential side effects of intranasal insulin (Schmid et al., 2018) at any time during the experimental protocol and the persistence of those symptoms. Additionally, the extent to which peripheral blood glucose was altered was also assessed via glucometer at the beginning of the session, during the middle of the exercise/sitting condition, and following the exercise/sitting condition

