Following removal of the eye blink components, stimulus-locked epochs were created for correct trials from -500 to 1,500 ms around the stimulus, baseline corrected using the -100 to 0 ms pre-stimulus period, and filtered using a zero phase shift low-pass filter at 30 Hz. Trials with artifact exceeding $\pm 100 \mu\text{V}$ were rejected. To ensure the integrity of the signal, stimulus-locked epochs were visually inspected blind to the experimental condition and dose prior to computing mean waveforms. Following visual inspection, the mean number of trials included in the waveforms was 112.0 [95% CI: 107.2 to 116.7] trials stimulus-locked to the congruent and incongruent trials (separately) of the Inhibitory Control task and 41.6 [95% CI: 40.1 to 43.2] trials stimulus-locked to the final stimulus of the target sequences of the Sustained Attention task.

Attention was indexed by the P3 ERP component. Attentional engagement was evaluated as the mean amplitude within a 50 ms interval surrounding the largest positive going peak within a 275 to 700 ms latency window following stimulus onset for the flanker task, and a 275 to 600 ms window for the RVIP task (Chandler et al., 2020; McGowan et al., 2019; Pontifex et al., 2015). Attentional processing speed was evaluated using ERP latency which was quantified as the time at which maximum peak amplitude occurred. Given the well-established nature of the P3 ERP component, analyses were conducted using a nine-channel region-of-interest approach centering around the topographic maxima of the P3 (i.e., the CP3/Z/4, P3/Z/4, PO5/Z/6 electrodes).

Aims Assessment:

- 1) *To provide a preliminary assessment of the safety profile of combining intranasal insulin with exercise; to ensure that undue risks are not incurred through combination therapeutic approaches.*

As the present investigation was a Phase II Clinical Trial, the research design is not sufficiently powered for hypothesis testing. Accordingly, this aim was satisfied by:

- A) Examining the frequency of participants reporting potential side effects of intranasal insulin at any time during the experimental protocol.
 - B) Examining the frequency of participants reporting potential side effects of intranasal insulin that persisted at the end of the experimental protocol.

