 - C) Examining the frequency of study discontinuations due to violations of the safety thresholds (e.g., blood glucose outside the range of 70 to 150 mg/dL, feeling dizzy, or unable to safety continue the experimental protocol).
- 2) *To provide a preliminary assessment of the efficacy of combining intranasal insulin with exercise for enhancing inhibitory aspects of cognitive control and sustained attention alongside neuroelectric indices of attention.*

As the present investigation was a Phase II Clinical Trial, the research design is not sufficiently powered for hypothesis testing. Accordingly, this aim was satisfied by computing the within subject effect size for each participant as the standardized change relative to the pretest assessment using the within-subject (d_{rm}) variance correction for Cohen's d (Lakens, 2013). To ensure the integrity of the effect size estimates, within-subject effect sizes exceeding 3 times the interquartile range were identified as outliers and removed from analysis. For each measure, within each experimental condition, the effect of intranasal insulin was corrected by subtracting the effect size observed for the 0 IU placebo group to isolate the effects of intranasal insulin. Preliminary assessments of the efficacy were thus quantified using:

- A) Effect size estimates with 95% confidence intervals for both control and exercise conditions collapsed across congruencies of the Flanker task to quantify the effects on **Behavioral Indices of Inhibitory Control**. Reaction time effects and response accuracy effects were separately extracted.
- B) Effect size estimates with 95% confidence intervals for both control and exercise conditions in response to the target trial of the Rapid Visual Information Processing task to quantify the effects on **Behavioral Indices of Sustained Attention**. Reaction time effects and response accuracy effects were separately extracted.

- C) Effect size estimates with 95% confidence intervals for both control and exercise conditions for P3 amplitude at the nine-channel region-of-interest to quantify the effects on **Neuroelectric Indices of Attentional Engagement**. Effects collapsed across congruencies of the Flanker task and effects for the target trial of the Rapid Visual Information Processing task were separately extracted.

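### Aim 1C counts discontinuations for high glucose, dizziness or inability to continue, but the written procedure states a stop only for glucose below 70 mg/dL

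*Combined protocol and SAP*

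**What the plan says.** Three parts of the combined protocol and SAP bear on this point.

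- **Aims Assessment, Aim 1, item C** defines the result as "Examining the frequency of study discontinuations due to violations of the safety thresholds". The thresholds follow as examples, introduced by e.g.: "blood glucose outside the range of 70 to 150 mg/dL, feeling dizzy, or unable to safety continue the experimental protocol".
- **Assessment day (day 2), after the description of the sitting and exercise conditions**, gives the stopping rule: "If peripheral blood glucose fell below 70 mg/dL, testing was immediately discontinued for all measures". The readings to which it can apply after dosing are taken "Midway through the sitting and exercise experimental conditions and again 5 minutes following the completion of the experimental conditions".
- **Assessment day (day 2), opening paragraph**, describes a glucose check on arrival, before any solution is given, "to ensure that their blood glucose fell within the 70-115 mg/dL guideline to exercise safely".

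Symptoms are collected once, at the end: "upon completion of the cognitive assessments, participants completed a symptom survey". Items A and B of Aim 1 count those symptoms at any time and at the end of the session. The Measures section also names change in peripheral glucose as part of the safety assessment.

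**The concern.** Item C counts decisions to stop, not glucose readings or symptoms. Its numerator therefore depends on the rule used in the session. If the definition of the count and the rule that generates it list different triggers, a reader cannot tell what a reported frequency means. A low number might mean that few participants crossed a threshold, or that crossing some of the thresholds did not lead to a stop.

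This matters because safety is the first aim and the plan says that "the research design is not sufficiently powered for hypothesis testing". The descriptive counts under items A to C are therefore the planned safety result, with no test behind them. Item C is also the only one of the three that refers to glucose. The Measures section names glucose change, but Aim 1 lists no summary of it.

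**Working it through.** The plan states no figure for this endpoint, so there is nothing to reproduce and no formula applies. The check sets the passages side by side, one kind of event at a time.

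| Event | Assessment-day procedure | Aim 1, item C | Consequence |
|---|---|---|---|
| Post-dose glucose below 70 mg/dL | Stop stated | Violation | Stopped and counted; the passages agree |
| Post-dose glucose above 150 mg/dL | No stop stated | Violation | No countable event under the written procedure |
| Dizziness | No stop stated; no in-session symptom check described | Violation | No countable event under the written procedure |
| Unable to continue safely | No stop stated | Violation | The session may end in practice, but no criterion is written |
| Arrival glucose above 115 and up to 150 mg/dL | Outside the arrival range | Inside the range | Occurs before dosing; not stated whether it counts |

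With the glucose range split into its two bounds, item C names four triggers: low glucose, high glucose, dizziness and inability to continue. One of the four, low glucose, has a matching rule. The 150 mg/dL limit appears nowhere else in the document.

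Two cases follow.

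1. *The procedure is complete.* Readings above 150 mg/dL and dizziness lead to no stop and so do not enter the count. Measured against its own definition, item C is then too low by the number of such participants, which is unknown.
2. *The procedure is not complete.* Staff also stopped sessions on other grounds. The count then depends on criteria that are not in the document, applied by experimenters who knew the activity and the number of doses from each vial, though not which vial held insulin.

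The document does not say which case applies, and in neither is item C fully defined. There are 7 doses and 2 activities, so the tally is spread over 7 × 2 = 14 cells. In cells of that kind, one or two events classified differently could change the picture. The document gives no cell sizes with which to go further.

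**The case against.** The strongest reply is that the passages can both be true. The procedure does not say that low glucose was the sole reason to stop, and the e.g. in item C suggests a partial list of criteria that were in force. This stands. A reader might infer that the procedure could never stop anyone for a high reading or for dizziness, so that these counts are zero by construction. That follows only if the stopping sentence is exhaustive, which the document does not say. The reply does not remove the gap, because an endpoint defined by an open list of examples is not fully defined.

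A reader might also infer three conflicting glucose limits. The documents do not support that. The 70-115 mg/dL range is a check before dosing and may properly differ from a limit that applies during the session. The lower bound of 70 is the same in all three places. The disagreement is over the upper limit and the symptom-based stops.

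Nor does the gap mean that high glucose or symptoms went unrecorded. Glucose was measured on arrival and twice after dosing, and symptoms enter items A and B. One reservation remains: the survey comes after the posttest tasks, and the document does not say whether participants who were stopped early completed it.

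Finally, it may be said that item C is descriptive, that both activities had the same reading times and the same stated rule, and that experimenters did not know which solution was insulin. All of this is correct, and nothing in the document shows a bias between arms. The point is the meaning of the count, not its direction.

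**Conclusion.** The mismatch is real and narrow. Item C counts stops for high glucose, dizziness and inability to continue, and the procedure gives no rule for any of them. Depending on whether the stopping sentence is complete, the tally either omits some of the events it claims to count or rests on unwritten criteria.

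The effect is confined to item C. It does not extend to items A and B or to the glucose readings themselves. Its size cannot be stated, because the document gives no glucose values, discontinuation counts or number of participants. The conclusion rests on the text alone and assumes that no separate operating procedure, outside this document, sets out the remaining stops. If one exists, the remedy is to bring its criteria into the plan.

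**What to change.** Reconcile the stopping rule under Assessment day (day 2) with Aim 1, item C, on the upper glucose limit and on symptom-based stops. Which limits and symptoms apply is for the sponsor to state, and this review takes no position. Replace the examples in item C with the full list of criteria that were in force.

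Then report under item C, for each dose and activity:

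- (i) participants with any post-dose reading outside the reconciled range, counted from the recorded readings whether or not testing stopped. Give the number with one and with two post-dose readings, because a session stopped midway may lack the second;
- (ii) discontinuations, by reason.

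Report failures of the arrival check, if there were any, on a separate line. The Screening Day text places allocation to activity and dose on day 1, so these are losses after randomisation but before dosing. They should not be counted as treatment events.

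Line (i) makes the glucose part of the tally independent of whether staff ended the session. The cost is a change of wording and a re-tabulation of readings that the protocol already schedules, with no new data collection. If reasons for stopping were not recorded at the time, the report should say so.

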- b. Participants must have normal or corrected-to-normal vision in order to complete the cognitive task.

Exclusion criteria: The following exclusion criteria exist for all participants:

- a. Lack of consent.
- b. Presence of any major neurological health issues, brain trauma, or concussion with loss of consciousness assessed through a health history and demographics questionnaire.
- c. Type I or Type II Diabetes.
- d. Self-reported pregnancy.
- e. Currently has any type of inflammation or blockage of the nasal passageways (i.e. allergies or a cold affecting the sinuses).
- f. Inability to engage in treadmill-based exercise.

Recruitment: Participants were recruited from the mid-Michigan community population via flyers and list-serve announcements.

Protocol: This investigation was approved by the Michigan State University Human Research Protection Program.

Screening Day (day 1): On the screening day of the testing protocol, following consenting to participate in this investigation; participants completed a brief health and history demographics questionnaire, a physical activity readiness questionnaire (Thomas et al., 1992), a medical screening questionnaire, the Wechsler Abbreviated Scale of Intelligence – 2nd Edition (WASI-II; (Wechsler, 2011), and a test of maximal oxygen uptake ($VO_2\text{max}$; using the same protocols as reported in (Chandler et al., 2019; Pontifex et al., 2016)). The medical screening questionnaire ensured that all participants were free of medication for high blood pressure, cholesterol, asthma, heart issues, depression/anxiety; and were not currently on any beta-blockers, sulfonamide antibiotics, corticosteroids, protease inhibitors, or Clonidine.

Participants who were eligible to continue in the study were then randomly assigned using a serial stratification approach accounting for biological sex to either an exercise [active experimental group] condition or sitting [control experimental group] condition. Within each condition; participants were subsequently randomly assigned using a serial stratification approach accounting for biological sex to receive a dose of either 0, 20, 40, 60, 80, 100, or 120 IU of fast acting insulin (Novolog Insulin Aspart 100 mg/mL) administered into the intranasal mucosa. Participants were instructed to refrain from exercise or caffeine intake, and too fast for at least 3 hours prior to participating in the second day of the testing protocol.

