Inhibitory Control Task: Inhibitory control was assessed using a letter version of the Eriksen flanker task (Eriksen & Eriksen, 1974; McGowan et al., 2019), which is classified as a behavioral response selection construct of the inhibition/suppression focus and the performance monitoring focus of cognitive control according to the NIMH Research Domain Criteria (RDoC) classification system. Participants were instructed to attend to and to respond as accurately as possible to a centrally presented stimulus nested amid either congruous ('MMMMM') or incongruous ('NNMNN') flanking stimuli. Participants completed 80 practice trials at pretest followed by 160 trials grouped into two blocks of 80 trials, each consisting of equiprobable congruency and directionality; at each assessment period (160 trials pre-experimental condition and 160 trials post-experimental condition). For each block of trials, participants were presented with perceptually similar letter pairs (e.g., pretest block 1: M – N, pretest block 2: E – F, posttest block 1: I – T, posttest block 2: U – V) and were instructed to respond by pressing the button assigned to the letter presented in the middle of the flanking letters.

To ensure a high degree of task difficulty, at the midpoint of each block participants were given instructions to reverse the button-letter assignments (e.g., left button press for “M” through the first 40 trials and then right button press for “M” through the last 40 trials). Flanking letters were presented 300 ms prior to the onset of the target letter, and all five letters remained on the screen for a subsequent 100 ms (for a total stimulus duration of 400 ms) with a response window of 1000 ms and a variable inter-trial interval of 2300, 2400, 2500, 2600, or 2700 ms. All stimuli were 1.5 cm tall white block letters presented focally on a black background. Stimulus presentation and timing were controlled using PsychoPy 1.86 (Peirce, 2009). Reaction time was quantified within each congruency as the mean speed of responding following the onset of the stimulus only for correct trials. Response accuracy was quantified within each congruency as the proportion of correct responses relative to the number of trials administered.

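### Efficacy intervals come from change scores minus the placebo effect size, with no covariates and no statement that placebo error is included; one pretest- and sex-adjusted model over the 14 cells would settle this at little cost

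*Combined protocol and SAP*

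**What the plan says.** Aims Assessment, item 2, bases efficacy on "computing the within subject effect size for each participant as the standardized change relative to the pretest assessment", using the d_rm form of Cohen's d. Extreme values are then dropped: "within-subject effect sizes exceeding 3 times the interquartile range were identified as outliers and removed from analysis". Next, within each condition, "the effect of intranasal insulin was corrected by subtracting the effect size observed for the 0 IU placebo group". The output for flanker behaviour is "Effect size estimates with 95% confidence intervals for both control and exercise conditions collapsed across congruencies of the Flanker task", and items B to D promise the same for the other measures.

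The section gives no interval formula, variance, degrees of freedom or resampling method. It does not say which participants supply the SDs and correlation for d_rm.

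Sex governs allocation. Under Screening Day (day 1), participants "were then randomly assigned using a serial stratification approach accounting for biological sex to either an exercise" or sitting condition, and dose is then allocated with the same stratification. Sex appears in no analysis.

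The same section of Aims Assessment says that "the research design is not sufficiently powered for hypothesis testing".

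**The concern.** Because testing is disclaimed, the estimates and intervals are the whole efficacy result. Two features deserve attention.

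- **Placebo error.** The 0 IU value is itself an estimate from one cell, and all six active doses in a condition share it. An interval for a placebo-corrected effect is valid only if it includes that cell's sampling error. The text is silent on this.
- **Unused covariates.** A change score fixes the pretest slope at 1. Regression on the pretest estimates the slope instead, and with equal pre and post SDs it usually gives a tighter contrast. Pretest and sex are already recorded.

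Items A to D list eight measures: reaction time and accuracy on two tasks, and P3 amplitude and latency on two tasks. If each active dose is reported separately, that makes 8 x 6 x 2 = 96 contrasts. If active doses were pooled it would be 8 x 2 = 16. The text does not settle which.

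**Working it through.** **Inputs.** From the documents: 7 doses x 2 conditions = 14 cells, and 95% intervals. Not given, so assumed: n = 4, 6, 8 or 10 per cell; r = 0.5 to 0.95; post/pre SD ratio s, first 1 and then varied; equal cells, normal data, one common scale, sex balanced within cells. The plan has no interval width or sample size to reproduce.

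**1. Variance of a dose-minus-placebo contrast (pretest SD = 1).**

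- Change score: (1 + s² - 2rs)(2/n), with 14n - 14 df if variance is pooled.
- Adjusted model: s²(1 - r²)(2/n)f², with 14n - 16 df. Here f is the SE inflation from estimating two slopes: 1.013, 1.007, 1.005, 1.004 at n = 4, 6, 8, 10.

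Both carry placebo error through the factor 2/n = 1/n + 1/n.

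**2. Equal SDs (s = 1).** The width ratio is about √((1 + r)/2), times a small-sample factor of 1.014 (n=4) to 1.004 (n=10).

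| r | √((1+r)/2) | model / pooled change-score width |
|---|---|---|
| 0.5 | 0.866 | 0.87-0.88 |
| 0.7 | 0.922 | 0.93-0.94 |
| 0.9 | 0.975 | 0.98-0.99 |
| 0.95 | 0.987 | 0.99-1.00 |

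Simulated half-widths at n=8, r=0.7 agree: 0.710 against 0.766, ratio 0.93. Coverage of both methods was 94.5-95.3%.

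**3. Unequal SDs (n=8, small-sample factor 1.0056).**

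- s=1.25, r=0.5: √(1.5625 x 0.75 / 1.3125) = 0.945, ratio 0.95.
- s=1.25, r=0.7: √(1.5625 x 0.51 / 0.8125) = 0.990, ratio 0.996.
- s=1.25, r=0.8: √(1.5625 x 0.36 / 0.5625) = 1.000, ratio 1.006.
- s=0.8, r=0.7: √(0.64 x 0.51 / 0.52) = 0.792, ratio 0.80.

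So the gain falls to nothing at r = 0.7-0.8 if the posttest SD is 25% larger, with a loss of about 1% at most, and it grows if the posttest SD is smaller.

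**4. One benefit, not two.** With s=1, 2(1 - r) = (1 - r²) + (1 - r)². At r=0.7 this is 0.60 = 0.51 + 0.09. The 0.09 is the chance pretest imbalance left in a change score. It is already inside the change-score variance, so removing it and gaining precision are the same thing.

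**5. Conditional check: placebo subtracted as a constant.** The true variance is then twice the one used, so coverage is P(|T| < t₀.₉₇₅/√2). At n=8 with the active cell's SD (7 df): 2.365/1.414 = 1.672, coverage 86.2%.

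| n | active cell's SD | pooled SD |
|---|---|---|
| 4 | 89.0% | 83.9% |
| 6 | 87.1% | 83.7% |
| 8 | 86.2% | 83.6% |
| 10 | 85.6% | 83.6% |

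If there are 96 contrasts, expected misses are 96 x (1 - coverage): 11-14 or 15-16, against 4.8. At n=8, r=0.7 the model's interval would be wider than the constant-placebo one: 0.710/0.624 = 1.14.

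**6. What the model assumes.** If one active cell's residual SD is 1.5 times the rest, the pooled interval covers 89-90%; HC3 covers 94-95%. If one cell's slope is 0.3 against 0.7 elsewhere (n=8), coverage is 93.7%, or 95.2% with HC3. With equal variances, HC3 intervals are 15, 9, 7 and 5% wider than the model's pooled ones at n = 4, 6, 8, 10. At n=8, r=0.7 the HC3 half-width of 0.758 is 0.758/0.766 = 0.99 of the pooled change-score width.

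**7. Sex.** At n=8, r=0.7, adding sex changes width by a factor of 1.000, 0.989, 0.971 or 0.943 if it explains 0, 2, 5 or 10% of residual variance (assumed shares).

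**The case against.** The strongest reply is that change scores are valid. They are unbiased under randomisation, a stable sex difference cancels in them, and one sentence confirming that placebo variance is included would repair the intervals without any new model. That stands: the coverage question alone does not require covariates. The case for the model is that it includes placebo error by construction and, for many plausible r, is tighter at trivial cost.

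Stronger readings are tempting but not supported:

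- **That the published intervals under-cover.** A reader might infer this from the order of steps. The text does not say that the placebo value is treated as a constant.
- **That the model is tighter whenever r is below about 0.9.** This needs roughly equal pre and post SDs, which the documents do not give, and enough people per cell. At 2 per cell the crossover is 0.79 with sex balanced and 0.66 with sex unbalanced at random.
- **That the model is safe whatever the data.** Its pooled interval has its own weakness under unequal variances, as step 6 shows.
- **That leaving out sex biases the contrasts.** It does not.

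It is also fair to say that the widths above are not those of the plan's exact estimator. They ignore outlier removal, and posttests that may be missing because testing stopped early. For the behavioural measures, a per-participant effect size could mean a scale built from that person's own trials. For P3 it could not, since amplitudes come from averaged waveforms ("stimulus-locked epochs were visually inspected blind to the experimental condition and dose prior to computing mean waveforms"). The need to include placebo error holds on either reading.

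**Conclusion.** The point holds as an inexpensive improvement that should be made, with medium confidence. What is certain from the text is that efficacy rests on unadjusted change scores minus a placebo estimate, and that the interval method is unstated. The size of the precision gain is conditional: worthwhile at r=0.5, modest at 0.7, negligible from 0.9 upward, under 4-10 per cell, equal pre and post SDs and a common scale. The coverage loss is a separate conditional: it applies only under constant-placebo subtraction, and repairing it would mostly widen the intervals. Sex adjustment helps only if sex predicts posttest given pretest.

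**What to change.** 1. For each measure, fit one linear model on the original scale over all 14 cells: posttest on pretest, sex, dose, condition and dose-by-condition. Report dose-minus-placebo contrasts within each condition with 95% intervals.
2. State and check the common pretest slope and residual variance. Show HC3 intervals alongside, above all for the accuracy outcomes, which are proportions ("Response accuracy was quantified within each congruency as the proportion of correct responses relative to the number of trials administered").
3. Keep everyone with data in the main fit. Apply the 3-IQR rule to residuals pooled over cells, and show results with and without removals.
4. If d_rm results are kept, include the placebo variance in their intervals and state whose SDs and correlation were used. If another unit-free value is wanted, divide every contrast by one common SD per measure and label it as different from d_rm.
5. Say whether each active dose is reported separately.
6. Label the work a reanalysis: Assessment day (day 2) and Neuroelectric Indices of Attention already report observed values.

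The cost is two degrees of freedom (98 to 96 at 8 per cell), the two added assumptions, some SAP wording and standard code. No new data are needed.
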